This study requires 8 visits to the clinic: a screening visit (week -1), a baseline visits (weeks 0, 1 and 2) and then follow up at 2, 4 and 12 weeks after starting the drug. Each visit will consist of blood draw. Subjects will be required to bring in a 24 hour urine sample on weeks 0, 4 and 12.

After the screening visit, subjects will be randomized into 2 groups. The first group will be started on 5 mg linagliptin (supplied by Boehringer Ingelheim Pharmaceuticals, Inc. (BIPI)) daily for 12 weeks. Fructosamine testing will be done at baseline, 4 and 12 weeks (and HbA1c at 0 and 12 weeks) to assess glycemic control. The second group will serve as a control group and will be placed on a placebo (mainly mannitol and corn starch, provided by BIPI in similar shape and color as the active drug) for 12 weeks. Blood samples will be obtained as described for patients on linagliptin. Each blood draw will consist of 45 ml of which 35 ml is collected in EDTA tubes and 10 ml in no-additive tubes. A single dose effect will be investigated at the first day of drug or placebo in 24 subjects (12 from each group) only and blood will be collected at 2, 4 and 6 hr following the first dose. The effect of a standard high-fat high-carbohydrate meal (HFHC) will be investigated on those 12 subjects from each group at baseline and at 12 weeks.

[figure not shown]

Figure 1: Study Design.

STUDY PROCEDURES BY VISIT:

Screening Day

Each subject will complete the following procedures and meet the inclusion and exclusion criteria prior to participating in the study.

1. Medical History
2. Physical Exam
3. Informed consent
4. Baseline lab draws to measure CBC, SMA, lipid profile, fructosamine and HbA1C

Visit 1: Week -2 to Week 0

Visit 1A: The participants will undergo HE clamp. They will be advised to bring 24 hour urine at this visit and research blood will be collected. All patients will have visit A. Visits B and C will be done only in 24 patients (12 in drug group and 12 in placebo group).

Visit 1B: The effect of a standard high-fat high- carbohydrate meal (HFHC) will be investigated in 24 subjects. Fat biopsy will be done before and after the meal.

Visit 1C (in 24 subjects): A single dose (5 mg or placebo) effect will be studied in 24 subjects with blood collections at 2, 4 and 6 hr following the first dose.

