Visits A, B and C will be separated by one week each. All patients will be randomized to drug or placebo groups on visit 1A but only patients who are not participating in visit 1B and 1C will start the drug or placebo at the end of visit 1A (considered week 0). Patients who are participating in visits 1B and 1C will start the drug or placebo at the beginning of visit 1C (considered week 0). Patient will return 2 weeks after starting drug or placebo. The drug will be started after these visits have been completed. Patient will return after 2 weeks.

Visit 2: Week 2

The participants will have their finger stick blood glucose records reviewed and blood will be drawn for labs. A container for 24 hour urine collection will be given. They will be advised to start collecting urine 24 hours prior to their next visit.

Visit 3: Week 4

The participants will have their finger stick blood glucose records reviewed and blood will be drawn for labs. 24 hour urine will be collected. They will be advised to start collecting urine 24 hours prior to their next visit.

Visit 4: Week 12

Visit 4A: The participants will have their finger stick blood glucose records reviewed. They will be advised to bring 24 hour urine at this visit and research blood will be collected. The participants will undergo HE clamp. All patients will have visit 4A.

Visit 4B: The effect of the HFHC meal will be investigated in 24 subjects who participated in visit 1B. Fat biopsy will be done before and after the meal.

Visits 4A and 4B will be separated by 2-5 days.

Compliance

The study coordinator will maintain a log of the entire study drug dispensed and returned.

Storage conditions: stored at room temperature in a locked cabinet.

Drug accountability: A master drug accountability log will be completed on arrival of supplies, Patient specific drug tracking logs will be completed including the following information: Date and amount of drug dispensed, initials of person dispensing study drug, date and amount of drug returned initials of

person receiving returned study drug.

Meal Challenge description

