This is a prospective study to evaluate oxidative stress before and after treatment with linagliptin. The similarities between the study groups, baseline values for subject's demographics will be compared using appropriate parametric tests. Transformations of the data on order to meet statistical assumptions may be considered. All statistical analysis will be carried out using SPSS software (SPSS Inc, Chicago, Illinois). Comparison of each endpoint will be made using an analysis of covariance model, with baseline medications, change in BMI and change in HbA1c as covariates. The primary endpoint of the study is to detect a change in JNK-1 protein in MNC before and after linagliptin use as compared to placebo. We have chosen this as the primary endpoint because JNK-1 is an inflammatory mediator that also interferes with insulin signaling. Our prior data with sitagliptin show a 24% fall (with SD of 24%) in JNK-1 following 12 weeks of treatment in type 2 diabetics(55). There was a 6% non-significant increase in JNK-1 protein in the placebo group in that study. Conservatively estimating a difference in change in JNK-1 cellular concentrations of 24% among the two groups, a sample size of 20 patients per group (assuming a drop-out rate of 15%) should provide adequate power ($\beta = 0.2$) to detect a significant difference ($\alpha = 0.05$), provided the standard deviation of the residuals is not equal to or greater than the mean difference (see table below).

Sample Size Estimate

Difference in the mean % change from baseline	Sample Size Estimate			
	5%	10%	15%	20%
10%	5	17	36	62
15%	3	8	17	28
20%	3	5	10	17

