Justification of drop-out rate: The analysis will adjust for only one baseline covariate: baseline medications. Two other covariates are change in BMI (which is not expected with linagliptin or placebo) and change in HbA1c. Sulfonylureas, metformin and subcutaneous insulin are not likely to induce insulin sensitization or decrease inflammation. Subjects currently on GLP-1 agonists or DPP-IV inhibitors will be excluded from the study. Thiazolidinediones can induce insulin sensitization as well as decrease inflammation. The use of thiazolidinediones should be equally distributed among the two groups. Less than 20% of our research subjects are on thiazolidinediones. Therefore it is likely that adjustment for thiazolidinediones should decrease sample size by <5%. Based on this justification and on our previous experience in diabetes trials, we have estimated that our drop-out rate will be 15% of 20 patients (3 patients per group).

The secondary endpoints for the study will be comparison of the relative change from baseline in a) inflammatory mediators in serum and adipose tissue, b) single dose effect of linagliptin on inflammation and oxidative stress, c) HFHC induced inflammation in serum and adipose tissue and d) insulin sensitivity and hepatic glucose output; before and after using Linagliptin for 12 weeks.

FACILITIES

LABORATORY: The Diabetes-Endocrinology Center of Western New York Research Laboratories at SUNY at Buffalo, contain 6 laboratories with space totaling approximately 1600 Qs ft designated for research purposes. These labs are dedicated for the P.I. research. There is a cold room, dark room and four labs have fume hoods. In addition, six offices (600 Qs ft) are attached to the labs for lab staff.

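### The primary ANCOVA omits baseline JNK-1, a value the endpoint already requires: precision is lost but validity is not, and the gain from adding it runs from substantial to nil

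*Combined protocol and SAP*

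**What the plan says.** The Data Analysis section compares each endpoint with an "analysis of covariance model, with baseline medications, change in BMI and change in HbA1c as covariates". Under the justification of the drop-out rate the list is closed: "The analysis will adjust for only one baseline covariate: baseline medications". The primary endpoint is the change in JNK-1 protein in mononuclear cells from before to after treatment, linagliptin against placebo.

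The pre-treatment sample exists in everyone. At visit 1A, "research blood will be collected. All patients will have visit A. Visits B and C will be done only in 24 patients". The remaining patients start study drug at the end of visit 1A. For the 24 in the sub-study, "Patients who are participating in visits 1B and 1C will start the drug or placebo at the beginning of visit 1C", and the visits are a week apart.

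JNK-1 protein is read by Western blot densitometry corrected for actin (Laboratory Procedures, Western blotting). No between-gel calibrator is described. The Figure 4 legend in the preliminary data reports JNK-1 as percent change.

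For the sample size, the earlier sitagliptin study showed a 24% fall with SD 24%, and "There was a 6% non-significant increase in JNK-1 protein in the placebo group in that study". The plan then works from "Conservatively estimating a difference in change in JNK-1 cellular concentrations of 24% among the two groups", with 20 patients per arm and 3 expected drop-outs in each.

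**The concern.** A change score subtracts baseline with a fixed slope of 1. ANCOVA estimates the slope. Unless pre- and post-treatment values are almost perfectly correlated, a high baseline tends to be followed by a larger fall, and the change score leaves that variation in the residual. Including baseline removes it.

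The plan makes its power claim conditional on a residual SD below the mean difference. Its planning SD (24) equals its planning difference (24), so the design sits on that boundary. Baseline adjustment acts directly on the residual SD.

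Only precision is at stake. Under randomisation, leaving out baseline JNK-1 neither biases the comparison on average nor inflates type I error. That statement concerns this omission alone; it does not assess the two covariates measured after randomisation.

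**Working it through.** **Inputs from the plan.** Difference 24 points; SD of change 24; alpha 0.05 (taken as two-sided); power 80%; 20 per arm less 3 drop-outs = 17 per arm, 34 in total.

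**Assumed.** The pre-post correlation r and the between-patient SD are not given. I take r from 0.3 to 0.95, with equal variances before and after treatment.

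**1. The plan's own figure.** Noncentrality = 24 / (24 × √(2/17)) = 2.915, df 32, critical t 2.037: power 80.7%. Seventeen is the smallest t-based size reaching 80%, and 17 / 0.85 = 20. The stated sample size reproduces. Power falls below 80% once the SD exceeds 24.2.

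**2. The plan's cushion.** The earlier study's gap was 24 + 6 = 30 points. At 30 points and SD 24, power is 94.2%, and the SD can reach 30.3 before power falls below 80%.

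**3. Adding baseline JNK-1.**
- Residual SD = 24 × √((1 + r)/2).
- The variance of the treatment estimate is multiplied by 31/30 on average because the slope is estimated; df 31.
- Fixing the SD of change at 24 implies a between-patient SD of 24 / √(2(1 − r)).

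Example, r = 0.5: residual SD 24 × √0.75 = 20.8; noncentrality 20.8 in place of 24 with the 31/30 factor = 3.31; critical t 2.040; power 89.4%.

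| r | Implied between-patient SD | Power at 24 points | Power at 30 points |
|---|---|---|---|
| not adjusted | – | 80.7% | 94.2% |
| 0.3 | 20% | 93.1% | 99% |
| 0.5 | 24% | 89.4% | 98% |
| 0.7 | 31% | 85.4% | 96% |
| 0.9 | 54% | 81.3% | 95% |
| 0.95 | 76% | 80.3% | 94% |

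At between-patient SDs of 40% and 50%, power at 24 points is 83% and 82%. Break-even is r = 0.93 (between-patient SD about 65%). As r approaches 1, power tends to 79.3%, a loss of 1.4 points.

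**4. With the three planned covariates in the model.** Assume one term each, unrelated to arm and outcome. Without baseline (df 29, variance factor 31/28), power at 24 points is 76.4%. With baseline (df 28, factor 31/27) it is 90.3%, 85.8%, 81.3%, 76.9% and 75.8% for the same five values of r. Break-even is r = 0.92.

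**5. Gel noise shared by a patient's two samples.** Such noise cancels in the change but contaminates the baseline covariate. If its SD equals the true between-patient SD, the observed correlation becomes (1 + r)/2, and adjusted power (without the planned covariates) is 86%, 84%, 82% and 80% for r = 0.3, 0.5, 0.7 and 0.9.

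A lognormal simulation on percent change (log SD of change 0.24, unadjusted power 88 to 89%) gave gains of 8, 6, 3 and 0 points at those values of r without gel noise. With shared gel noise of log SD 0.4, the gain was about one point or less at every r.

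**6. Simulation check of steps 3 and 4.** With 10,000 trials per setting, adjusted power without the planned covariates was 93.4%, 89.3%, 85.5%, 81.6% and 79.8%. Type I error was 0.045 to 0.054 in all models, and mean estimates were 23.9 to 24.2, which supports no bias.

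**7. Sub-study endpoints.** With 12 per arm, break-even falls to r of about 0.90, before allowing for drop-out or the planned covariates.

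**The case against.** The strongest objection is that the gain may not exist. The plan describes actin correction but no calibrator between gels, and both the Figure 4 legend and the sample-size table work in percent change. If readings are stored only relative to the patient's own baseline, every baseline is 100% and there is nothing to adjust for. If raw readings are kept but gels differ widely, the simulated gain is about nil. This stands: the benefit is conditional, and it needs no new work only if readings are already comparable.

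Second, the large gains depend on an undocumented r. The 93% figure needs patients to differ by only about 20% SD at baseline; at 40% to 50% the gain is 1 to 2 points. At the observed 30-point gap it is 0 to 5 points on a base of 94%. This also stands, which is why a range is shown.

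Third, the figures with the planned covariates are idealised. Baseline medications may need several terms, and change in HbA1c is unlikely to be unrelated to arm when the plan itself expects better glycaemic control on linagliptin. Those figures are illustrative only.

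Fourth, with no bias and stated power met, this could be called optional. I still recommend it, because the trade is lopsided: up to about 12 points gained over the range shown, against at most 1.4 lost, for one prespecified line.

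**Conclusion.** The concern holds. Baseline JNK-1 is explicitly outside the primary model although every patient's endpoint requires it. The cost is precision only. At 17 per arm and a 24-point difference, including it takes power from 80.7% to between 80% and 93% as r goes from 0.95 to 0.3. The gain is smaller at 30 points and about nil when r exceeds 0.93 or when shared gel noise is large. These figures rest on equal variances, an SD of change of 24, and an assumed r.

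This is not a failure of the sample size, which reproduces and carries a cushion of 30 observed against 24 planned. The change should be made, with medium confidence in its size because the documents do not settle r or the comparability of the blots.

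**What to change.** - Add each patient's visit 1A actin-corrected JNK-1 value as a covariate in the primary ANCOVA, and name visit 1A as the analysis baseline for all patients. In the 24 sub-study patients it precedes first dose by about two weeks, so the choice should be explicit.
- State that actin-corrected readings will be kept on a scale comparable across patients and gels. If they will exist only as a percentage of the patient's own baseline, this change does not apply.
- For each secondary endpoint, add its own pre-treatment value in the patients who have it, and name that sample for the meal and single-dose endpoints. The plan lists blood at 2, 4 and 6 hours after the first dose without naming a pre-dose sample.
- A log scale is optional and already permitted: "Transformations of the data on order to meet statistical assumptions may be considered".

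Cost: one degree of freedom in the primary model and a few lines of text. The primary analysis needs no new patient samples. If readings are not now comparable across gels, a laboratory step such as a common calibrator sample is needed before there is any benefit. The other covariates are outside this point.

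### The plan expects thiazolidinedione use to be equal between arms, but the randomisation it describes has no step to secure this; the cost is a modest loss of precision that stratification would largely avoid

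*Combined protocol and SAP*

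**What the plan says.** The inclusion criteria admit thiazolidinedione users whose dose is stable and stays unchanged during the study. The paragraph on drop-out rate in Data Analysis regards sulfonylureas, metformin and insulin as unlikely to matter, but says of this class: "Thiazolidinediones can induce insulin sensitization as well as decrease inflammation". It continues: "The use of thiazolidinediones should be equally distributed among the two groups". It gives the prevalence as "Less than 20% of our research subjects are on thiazolidinediones", and concludes that adjusting for the class will probably cost less than 5% of the sample size.

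The allocation is described in Study Population, Study Design and Visit 1 of Study Procedures by Visit. The fullest statement is "All patients will be randomized to drug or placebo groups on visit 1A". None of these sections mentions stratification, blocking or minimisation.

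Data Analysis compares each endpoint by analysis of covariance, with baseline medications, change in BMI and change in HbA1c as covariates. It does not say how baseline medications are coded.

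**The concern.** The plan identifies a background drug class that may act on the same processes as the study drug, expects it to be evenly spread, and leaves the spread to chance. Randomisation balances the class in expectation. With a handful of users among 40 patients, a single allocation can still be visibly uneven.

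What is at stake is limited. When a covariate is correlated with treatment arm, adjusting for it widens the standard error of the arm difference. The sample size has almost no slack to absorb this. A lopsided split would also invite questions about the result, more so if the medications covariate turned out not to separate thiazolidinediones from other drugs.

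**Working it through.** **Inputs from the plan (Data Analysis)**
- 20 patients per group. Drop-out: "we have estimated that our drop-out rate will be 15% of 20 patients (3 patients per group"; this leaves 17 completers per group.
- Difference in percentage change of JNK-1: 24 points. SD from the earlier sitagliptin study: 24 points.
- Alpha 0.05 and power 80%. Sidedness is not stated; two-sided is assumed here.
- Thiazolidinedione use below 20%. Since 0.20 × 40 = 8, eight users is the ceiling, not the expected number.

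**Step 1. The plan's own sample size.** A two-sample t-test with difference 24 and SD 24 needs 17 per group (exact power 80.7%). Then 17 / 0.85 = 20. The stated figure reproduces.

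**Step 2. Precision cost of a given split.** With K users among 40, a of them in one arm and b in the other, and 20 patients per arm, the squared correlation between arm and use is

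r² = (a − b)² / [K(40 − K)]

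and the variance of the adjusted arm difference is multiplied by 1/(1 − r²). For 8 users:
- 5-3: r² = 4/256 = 0.0156, inflation 1.016
- 6-2: r² = 16/256 = 0.0625, inflation 1.067
- 7-1: r² = 36/256 = 0.1406, inflation 1.164

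**Step 3. How often inflation exceeds 5%.** The number of users falling in one arm is hypergeometric (40 patients, K users, 20 per arm).

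| Users K | Narrowest split with inflation above 5% | Inflation at that split | Probability of that split or wider | Mean inflation |
|---|---|---|---|---|
| 4 | 4-0 | 12.5% | 10.6% | 2.8% |
| 5 | 4-1 | 5.4% | 34.2% | 2.8% |
| 6 | 5-1 | 8.5% | 18.2% | 2.8% |
| 7 | 6-1 | 12.1% | 9.1% | 2.8% |
| 8 | 6-2 | 6.7% | 23.5% | 2.8% |

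The probabilities are not monotone because only whole-number splits are possible. At 5 users, for example, 4-1 only just passes the threshold. With coin-flip allocation instead of fixed 20/20 arms, the probability of 6-2 or wider among 8 users is 74/256 = 28.9%.

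If the number of users is itself random, at assumed prevalences of 10%, 15% and 20%, the chance of inflation above 5% is 22.7%, 20.2% and 18.4%.

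**Step 4. Effect on power.** With 17 completers per group, difference 24 and SD 24 (noncentral t, variance multiplied by the inflation, which is computed on the 20/20 allocation):
- no inflation: 80.7%
- mean inflation of 2.8%: 79.6%
- 6-2 split (6.7%): about 78%
- 7-1 split (16.4%): about 75%

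These figures leave out the other covariates. They also leave out any reduction in residual SD from adjusting for a prognostic factor, which would offset part of the loss.

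**Step 5. The substudy.** With 12 per arm and an assumed 5 users (slightly above 20% of 24), the chance of 4-1 or wider is 31.7%, and the inflation at 4-1 is 10.5%.

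**The case against.** The strongest reply is that the analysis already deals with the matter. The covariance model adjusts for baseline medications, and the drop-out paragraph speaks of adjusting for thiazolidinediones by name. A plan that adjusts does not depend on equality for validity. This stands. A reader might infer that an uneven split would bias the treatment comparison; the documents do not support that, provided the medications covariate carries thiazolidinedione use as a separate term.

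Second, the plan says only that a cost below 5% is likely. That is correct without any stratification: average inflation is about 2.8%, and 66% to 91% of allocations stay within the allowance for 4 to 8 users. It would be wrong to read the 6-2 or 7-1 figures as refuting the plan.

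Third, the one-in-four probability of a 6-2 split applies to exactly 8 users, which the plan's wording puts at or just beyond the limit. With 7 users, a 5-2 split inflates variance by only 4.1%, and 6-1 or wider has probability 9.1%. The range should be quoted, not the single figure. Fewer users does not remove the issue, however, as the rows for 4 to 6 show.

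Fourth, the plan does not say that thiazolidinediones alter JNK-1. The primary endpoint is a change from baseline, and doses must stay stable, so a constant effect on level would largely cancel. This weakens any claim about the size of the effect on the primary result. It does not alter the precision arithmetic, which depends only on the split.

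Finally, covariate adjustment in place of stratification is a legitimate choice in a 40-patient mechanistic trial. That is why this is a suggested improvement and not an error.

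**Conclusion.** The point holds as a modest design weakness. The plan expects balance in a factor that it considers relevant and includes no step to obtain it. For 4 to 8 users and 20/20 allocation, the chance that adjustment costs more than 5% in variance is between 9% and 34%. The usual cost is small: about one percentage point of power on average, and between two and three points at a 6-2 split. Because the sample size sits almost exactly at 80% power, even these losses bring it below target under the plan's own difference and SD.

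The result rests on the prevalence ceiling carrying over from the centre's research subjects to this trial, on a two-sided test, on 17 completers per group, and on thiazolidinedione use being coded as its own covariate. The last of these is not stated in the plan.

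**What to change.** Stratify the Visit 1A randomisation by thiazolidinedione use (yes or no, recorded in the screening history), using permuted blocks concealed from site staff. State in Data Analysis that the same indicator enters the covariance model as its own term within baseline medications.

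The cost is a second randomisation list and possibly an incomplete block in the small stratum of users. No extra patients, visits or procedures are needed.

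Stratifying the 40 does not by itself balance the 24 patients in the meal and single-dose substudy, because that depends on who takes part. The thiazolidinedione term should be used in those analyses too, and the split among the 24 reported.
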